##### 1.1.2 Missing and BQL Concentrations

Missing values will not be used in any way.

For calculation of all pharmacokinetic parameters and individual profile plots, plasma concentrations below the quantifiable limit (BQL) of the assay will not be used for the calculation of PK parameters (except BQL values observed at time points before the maximum concentration, which will be taken as zero).

BQL values will be substituted by one half of the lower limit of quantification for calculation of plasma concentration summary statistics. The number of imputed values will be included in the summary table.

For urine concentrations reported as BQL it is not possible to impute a value. The amount excreted will be set to zero when concentration is BQL.

#### 1.2 AUC Calculations

The AUC will be calculated by a combination of linear and logarithmic methods. The linear trapezoidal method will be employed for all incremental trapezoids arising from increasing concentrations and the logarithmic trapezoidal method will be used for those arising from decreasing concentrations

AUC(0-∞) values with <20% of this area extrapolated will be reported.

It is acceptable to include data from profiles with >20% extrapolated as long as at least 80% of the profiles in the study have <20% of the  $AUC_{(0-\infty)}$  as extrapolated area. In this instance, individual plasma concentration-time profiles for which the extrapolated areas are >20% of  $AUC_{(0-\infty)}$  will be identified.

It is unacceptable to use  $AUC_{(0-\infty)}$  data if >40% of the AUC has been extrapolated, except in specific situations which should be carefully justified in the study report.

### 1.3 Lambda-z Calculations

The apparent terminal phase rate-constant ( $\lambda_z$ ) will be estimated by linear regression of logarithmically transformed concentration versus time data. Only those data points which are judged to describe the terminal log-linear decline will be used in the regression.

During the analysis, repeated regressions are carried out using the last three points with non-zero concentrations, then the last four points, last five, etc. Points prior to  $C_{max}$  are not used. Points with a value of zero for the concentration are excluded. For each regression, an adjusted  $R^2$  is computed. The  $\lambda_z$  using the regression with the largest adjusted  $R^2$  is selected. If the adjusted  $R^2$  does not improve, but is within 0.0001 of the largest adjusted  $R^2$  value, the regression with the larger number of points is used.  $\lambda_z$  must be positive, and calculated from at least three data points.

For non-compartmental analysis uniform weighting will be applied.

### 1.4 Observed v Predicted Values

For parameters dependent on  $\lambda_z$ , the ‘predicted’ rather than the ‘observed’ parameters will be calculated.

The ‘predicted’ parameters are calculated using  $\hat{C}_t$  (the predicted value of the concentration at time  $t_n$ ); whilst the ‘observed’ parameters use the last observed concentration.

## **2 General Considerations for Data Analysis**

### **2.1 Derived and transformed data**

In general, concentration and concentration-related quantities, rate constants and half-lives (e.g.  $C_{\max}$ , AUC,  $t_{1/2}$ , CL/F,  $V_z/F$  and MRT) will be analysed after logarithmic transformation. Logarithmic transformations will use natural logarithms ( $\log_e$ ). A list of those parameters that will be log transformed are given below.

### **2.2 Summary data**

Means at any time will only be calculated if at least 2/3 of the individual data are measured and are above the lower of quantification (LLOQ).

CONFIDENTIAL

### 3 Parameter Definitions

#### 3.1 Plasma Parameters

##### 3.1.1 Emodepside

Text Symbol	Definition	Calculation	Typical Units	Log Transform	WNL	CDISC Controlled Terminology	TFL Symbol
Concentrations and times							
$C_{max}$	Maximum (peak) plasma concentration	The maximum (peak) plasma concentration will be obtained directly from the concentration-time data.	ng/mL	Y	Cmax	CMAX	$C_{max}$
$C_{max}/D$	Dose-normalised $C_{max}$ to infinity	The dose-normalised $C_{max}$ will be calculated as $C_{max}/\text{Dose administered}$	(ng/mL)/mg	Y	Cmax_D	CMAXD	$C_{max}/D$
$C_{max,norm}$	Observed maximum plasma concentration corrected by dose and body weight	The $C_{max}$ normalised by dose and body weight will be calculated as $C_{max}/(\text{Dose administered}*\text{body weight})$	(ng/mL)/(mg*kg)	Y	N/A	CMAXWD	$C_{max,norm}$
$t_{max}$	Time to reach maximum (peak) plasma concentration	The first time of maximum (peak) plasma concentration will be obtained directly from the concentration-time data.	h	N	Tmax	TMAX	$t_{max}$
Half-life							
$\lambda_z$	Terminal rate constant	The apparent terminal phase rate-constant ( $\lambda_z$ ) will be estimated by linear regression of logarithmically transformed concentration versus time data.	1/h	Y	Lambda_z	LAMZ	$\lambda_z$
Point terminal	Number of points for Lambda z	The number of time points used in calculating Lambda z	-	-	No_points_lambda_z	LAMZNPT	$n_{pts}$
$t_{1/2}$	Terminal half-life	The terminal half-life calculated from the terminal slope of the log concentration-time curve, as follows: $t_{1/2} = \frac{\log_e 2}{\lambda_z}$	h	Y	HL_Lambda_z	LAMZHL	$t_{1/2}$
$t_{1/2,0-24}$	Dominant half-life	The half-life calculated from the terminal slope of the log concentration-time (0-24h) curve, as follows: $t_{1/2} = \frac{\log_e 2}{\lambda_z}$	h	Y	HL_Lambda_z	TBC	$t_{1/2,0-24}$

Text Symbol	Definition	Calculation	Typical Units	Log Transform	WNL	CDISC Controlled Terminology	TFL Symbol
Areas under the curve							
AUC t	Area under the plasma concentration-time curve from time zero to time of last measurable concentration	The area under the concentration-time curve from zero time (pre-dose) to the time of last quantifiable concentration will be calculated using the (specified) trapezoidal method.	h*ng/mL	Y	AUClast	AUCLST	AUC last
AUC t,norm	Area under the concentration-time curve from time zero (pre-dose) to the time of last quantifiable concentration corrected by dose and body weight	The AUC normalised by dose and body weight will be calculated as AUC t /(Dose administered*body weight)	(h*ng/mL)/(mg*kg)	Y	N/A	AUCLSTWD	AUC last,norm
AUC t-∞	Area under the exponential curve from t last to infinity	The area under the exponential curve from t last to infinity, calculated as follows: $AUC_{t-\infty} = \frac{\hat{C}_t}{\lambda_z}$ where $\hat{C}_t$ is the predicted value of the concentration at t last .	h*ng/mL	N/A	N/A	AUCIFO	AUC t-inf
AUC ∞	Area under the plasma concentration-time curve from time zero to infinity	The area under the concentration-time curve will be calculated using the (specified) trapezoidal method for the interval 0 to t last (time t last is the time at which the last non-zero level was recorded), plus AUC t-∞ .	h*ng/mL	Y	AUCINF_pred	AUCIFP	AUC inf
AUC ∞ /Dose	Dose-normalised AUC to infinity	The dose-normalised AUC to infinity will be calculated as AUC ∞ /Dose administered	(h*ng/mL)/mg	Y	AUCINF_D_pred	AUCIFPD	AUC inf /D
AUC ∞,norm	Area under the concentration-time curve from time zero to infinity corrected by dose and body weight	The AUC normalised by dose and body weight will be calculated as AUC ∞ /(Dose administered*body weight)	(h*ng/mL)/(mg*kg)	Y	N/A	AUCIFPWD	AUC inf,norm
%AUC extrap	Percentage of AUC ∞ extrapolated from from t last to infinity	$\%AUC_{extrap} = \frac{100 \times AUC_{t-\infty}}{AUC_{\infty}}$	%	N	AUC_%EXTRAP_pred	AUCPEP	%AUC extrap

Text Symbol	Definition	Calculation	Typical Units	Log Transform	WNL	CDISC Controlled Terminology	TFL Symbol
AUC 0-24	Area under the plasma concentration-time curve from time zero to 24h	The area under the concentration-time curve from zero time (pre-dose) to 24h will be calculated using the (specified) trapezoidal method.  If $\lambda_z$ is not estimable, a partial AUC is not calculated (when $t_{last} < t$ ).	h*ng/mL	Y	User specified area	AUCINT	AUC 24
AUC 0-24 /D	Dose-normalised AUC from time zero to 24h	The dose-normalised AUC from time zero to 24h will be calculated as AUC 0-24 /Dose administered	(h*ng/mL)/mg	Y	N/A	AUCINTD	AUC 24 /D
AUC 0-24,norm	Area under the concentration-time curve from time zero to 24h corrected by dose and body weight	The AUC from time zero to 24h normalised by dose and body weight will be calculated as AUC 0-24 /(Dose administered*body weight)	(h*ng/mL)/(mg*kg)	Y	N/A	AUCINTWD	AUC last,norm
Clearance, volume of distribution and mean residence time							
CL/F	Apparent total clearance from plasma after oral administration	Apparent total clearance from plasma will be calculated using the following formula: $CL/F = \frac{Dose}{AUC_{\infty}}$	L/h	Y	Cl_pred (actually derives Cl_F_pred for oral dose)	CLFP	CL/F
V z /F	Apparent volume of distribution during terminal phase after non-intravenous administration	Apparent volume of distribution will be calculated using the following formula: $V_z/F = \frac{Dose}{\lambda_z \cdot AUC_{\infty}}$	L	Y	Vz_pred (actually derives Vz_F_pred for oral dose)	VZFP	V z /F
MRT	Mean Residence Time	The mean residence time will be calculated using: $MRT = \frac{AUMC}{AUC_{\infty}}$	h	Y	MRTINF_pred	MRTIFP	MRT
AUMC	Area under the first moment of the plasma concentration-time curve from time zero to infinity	The area under the first moment of the concentration-time curve from zero time (pre-dose) extrapolated to infinite time will using the (specified) trapezoidal method, as for AUC.	h  *ng/mL	-	AUMCINF_pred	AUMCIFP	AUMC

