- 28 days rats study: NOAEL = 5 mg/kg ➤ 0.048 mg/kg
- 28 days dog study: NOAEL = 5 mg/kg ➤ 0.075 mg/kg
- Single administration rat: NOAEL = 10 mg/kg ➤ 0.035 mg/kg

The 1.75 mg dose is not practical in the Liquid Service Formulation (LSF, solution), and it is not recommended to dose the LSF in less than 0.5 mL (0.5 mg) increments. The dose of 1.0 mg is chosen as the starting dose. Therefore, two dose steps are required to reach the 5 mg dose (tablet).

Estimation of Human Exposure to Emodepside

The prediction of human PK was based on the data obtained from in vivo experiments after administration of emodepside to rats and dogs and from in vitro data (plasma protein binding, blood/plasma partitioning).

The classical allometric species scaling approach (with fu correction) including both species resulted in implausible values for the exponent for both CL and V_{ss} . Therefore, the key parameters CL and Vss were assessed by single species scaling.

In order to predict human PK parameters and c/t profiles, rat and dog plasma concentrations after intravenous and oral administration were fitted to a 3 compartment model using Phoenix 6.3. In order to obtain a better fit the 96h values of the rat PK data were excluded. Fitted single parameters for CL, CLD1, CLD2, Vc, Vt1 and Vt2 were scaled to humans considering fu and using the fixed exponent approach with an exponent of 1 for scaling of volumes and 0.75 for scaling of clearances. The bioavailability used for the prediction of the oral concentration vs. time profiles in man was with 50% about the mean value from bioavailabilities observed in animal species.

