The predicted human CL is low for both species used for prediction. The differences in predicted human clearance ranging from 0.11 (rat) to 0.14 L/(kg·h) (dog) are minor. With the Cb/Cp distribution of 0.6 values for CLblood would be 0.18 (rat) and 0.23 (dog), respectively. These predictions are in the same range as the human clearance obtained in vitro in hepatocytes (CLblood = 0.36 L/(kg·h)). The predicted volume of distribution in man is high covering a range of 15 L/kg (rat) to 11 L/kg (dog). However, individual parameters for volume (Vc, Vt1 and Vt2) showed differences according to the species used for prediction. Consequently, the C/t profiles predicted for man mainly differ in C_{max} and t_{max} . The value for the absorption rate constant (ka, 0.8 h-1) was based on former experiences with PEG-based liquid service formulations. The bioavailability obtained from the animal species was directly used for the prediction of the human plasma concentration profiles.

Description of the theoretical dose levels to be studied is presented in Table 2:

Table 2. Study Treatment: Formulation and Dose-Levels by Cohort

Part	Cohort	Formulation	Do	ose	Increase from
			Total mg	mg/kg ^a	Previous Dose
	Cohort 1	LSF solution	1.0	0.014	
	Cohort 2	LSF solution	2.5	0.036	+ 150%
	Cohort 3	LSF solution	5.0	0.071	+ 100%
1	Cohort 4	IR tablet	5.0	0.071	+ 100%
'	Cohort 5	LSF solution	10.0	0.143	+ 100%
	Cohort 6	LSF solution	20.0	0.286	+ 100%
	Cohort 7	IR tablet	20.0	0.286	+ 100%
	Cohort 8	LSF solution	40.0	0.571	+ 100%
2 ^b	Cohort 9	LSF solution (fed)	10.0	0.143	Not applicable
	Cohort 10	LSF solution	40.0	0.571	Not applicable

^a Dose levels are theoretical, as calculated based on an average weight of 70kg.

^b Part 2 (Cohorts 9 and 10) are considered exploratory

4. Selection of Subjects

The following eligibility criteria were designed to select healthy male subjects aged 18 to 55, selected from the panel of volunteers recruited by HMR, for whom the protocol treatment is considered appropriate. All relevant medical and non-medical conditions should be taken into consideration when deciding whether this protocol is suitable for a particular subject. Eligibility criteria may not be waived by the Investigator. Any questions regarding a subject's eligibility should be discussed with the Sponsor's Medical Expert prior to subject's enrolment.

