ECGs extracted from continuous recordings ⁹													X ^g	X ^g	X ^g	Χ ^g	X ^g	X ^g	X ^g	Χ ^g		Χ ^g	X ^g	X ^g	Χ ^g												
Vital signs ^h	Х		X ^h	Χ	Х	Χ	X ^h	Χ	X ^h	Χ	Χ	X ^h	X ^h	Χ	Χ	Χ	X ^h		Χ	X ^h		Х	Χ	X ^h	X ^h	Χ	Χ	Χ	Χ	Χ	Χ	Χ					Х
Adverse event monitoring ⁱ	Х	Х	Х				Х		Х			Χ	Х		Х		Χ		Х	Х		Х	Χ	Х	Х	Х	Χ	Х	Χ	Х	Х	Х					Χ
PK and metabolites in plasma													X ^j	Χ	X ^j	Х	X ^j	Х	Х	X ^j		Х	X ^j	X ^j	X ^j	Χ	X ^j	Х	Χ	Х	Х	Х					Χ
PK in urine ^k			1	l	1											0-4 ^k					4–8 ^k		8–12 ^k	12-24 ^k												一十	
Laboratory Safety ^{I,m}	Χ ^m		Х										Χ												Χ		Χ	Χ	Χ	Χ	Х	Χ					Χ
Neurological ^d examination and short physical examination ^c			Xc				Х		Х			Х	Х				Х			Х				Х	Х	Х	Х										

- *: In fasted subjects, all assessments at Hour –24 on Day –1 and Hour 0 on Day 0 are immediately before the administration of study drug (emodepside). In fed subjects, all assessments at Hour –24 on Day –1 and at Hour 0 on Day 0 are before the FDA breakfast. The only exception is the 12-lead ECG continuous recording (see footnote g).
- a: Including a 10-minute supine phase before supine BP, HR, body temperature, ECG; and for 5 minutes after each nominal timepoint for ECGs extracted from continuous recording (see footnote); and also recommended before drawing blood samples. Before sitting BP assessments minimum 3-minute sitting period.
- b: If mean half-life of emodepside in any cohort is longer than predicted, there are options to extend in-house period, or out-patient ambulatory visits up to Day 14 if necessary, from Cohort 5 onwards and in subsequent cohorts. Refer to Option 1, Option 2, and Option 3 as outlined in Table 4.
- c: Height at screening only, for calculation of BMI. Weight at screening for calculation of BMI, also at -24h (Day -1) for PK calculations.
- d: Neurological examination designed for the study, see Section 8.19.4 and Study Procedures Manual
- Administration of study drug while fasting or after a high-calorie, high-fat breakfast
- . To include 3 repeat ECGs at these timepoints, with a time difference of about 1 minute, and single recordings at other timepoints

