## 15 Changes from the Protocol Specified Statistical Analysis

After the study was submitted to the MHRA and ethics committee the following changes were made to the analyses:

- 1) The definition of treatment-emergent adverse event has been updated from “an AE will be considered as treatment emergent if it appeared after the first dosing, or if appeared before dosing and worsened after dosing” to:

A treatment-emergent adverse event is defined as an event emerging during treatment having been absent pre-treatment or having worsened relative to pre-treatment.

- 2) The  $AUC_{0-24}$  of change from baseline for glucose, insulin, glucagon and cortisol will be summarised for each day and treatment

- 3) The following emodepside parameters have been added to those mentioned in the protocol:

Main PK parameters:  $AUC_{0-24}$  and  $AUC_{0-24}/D$

Exploratory PK parameters:  $AUC_{0-24, norm}$ ,  $t_{1/2, dom}$

- 4) The following analyses have been added for glucose, insulin, glucagon and cortisol:

The difference between change from baseline on Day 0 and Day -1 will be summarised at each planned post-baseline assessment by actual treatment

The  $AUC_{0-24}$  of change from baseline will be summarised for each day and treatment

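### Four exploratory PK parameters are divided by dose × body weight instead of dose per kg, which adds weight dependence instead of removing it

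*SAP*

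**What the plan says.** SAP Appendix B, section 3.1.1, has four rows for parameters adjusted for both dose and weight. The AUCt row reads "The AUC normalised by dose and body weight will be calculated as AUC t /(Dose administered*body weight", the AUC∞ row "The AUC normalised by dose and body weight will be calculated as AUC ∞ /(Dose administered*body weight" and the 24-hour row "The AUC from time zero to 24h normalised by dose and body weight will be calculated as AUC 0-24 /(Dose administered*body weight". The Cmax row uses the same construction. The units column gives (ng/mL)/(mg*kg) for Cmax,norm and (h*ng/mL)/(mg*kg) for the three AUCs. The SAP file carries its text twice, and both copies agree.

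The protocol (section 8.16) says only that these quantities are adjusted for dose and weight, and gives no formula. Where it combines dose and weight itself, it uses mg/kg. Table 2 in section 3.3 shows each flat dose on a mg/kg scale, with the footnote "Dose levels are theoretical, as calculated based on an average weight of 70kg". Table 3, footnote c, has weight measured at screening and "also at -24h (Day -1) for PK calculations".

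Cmax,norm, AUCt,norm and AUC∞,norm are exploratory in both documents. SAP section 15 adds AUC0-24,norm under "Exploratory PK parameters". That section lists departures from the protocol and does not mention a product form.

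**The concern.** The label and the formula disagree. A reader who sees a weight-adjusted exposure expects differences in body size to have been largely taken out. With a flat dose, dividing by weight pushes a heavy subject's value, which would normally already be lower, further down. Following the SAP exactly would put four parameters into the report that depend more on weight than the simple dose-normalised versions beside them. Their between-subject CVs would be inflated. Their values would also not be comparable with anything expressed per mg/kg.

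**Working it through.** **Formula against units.** AUC/(dose × weight) has units (h*ng/mL)/(mg*kg), exactly as printed. Formula and units agree in all four rows and in both copies, so this is not a text-extraction fault.

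**The protocol's own convention.** Table 2 reproduces as dose/70: 1, 2.5, 5, 10, 20 and 40 mg give 0.014, 0.036, 0.071, 0.143, 0.286 and 0.571 mg/kg. The protocol also states clearance in L/(kg·h) (sections 1.2 and 3.3). The SAP sets CL/F = Dose/AUC∞, so AUC∞ × weight / dose is the reciprocal of apparent clearance per kg, the scale on which the protocol works. AUC∞/(dose × weight) is the reciprocal of clearance multiplied by weight, which appears nowhere else.

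**Scale.** Protocol section 1.3 gives a mean AUC of 4315 ng·h/mL and Cmax of 612 ng/mL at 40 mg. At an assumed 70 kg:
- as written: 4315/(40 × 70) = 1.54 and 612/(40 × 70) = 0.219
- dose per kg: 4315/(40/70) = 7551 and 612/(40/70) = 1071

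The two forms differ by weight squared (70² = 4900).

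**Weight dependence.** Let X/Dose be proportional to W^(−b). Then:
- X/Dose has exponent −b
- the SAP form X/(Dose × W) has exponent −(b + 1)
- dose per kg, X × W/Dose, has exponent 1 − b

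The documents give no human weight–exposure relationship, so b is an assumption. The nearest anchor is protocol section 3.3, which used "an exponent of 1 for scaling of volumes and 0.75 for scaling of clearances"; those are cross-species exponents. The weights are also assumed. The pair 100 and 60 kg has ratio 1.667, close to the widest ratio that the BMI criterion allows at one height (30.1/18 = 1.672). The pair 85 and 65 kg has ratio 1.308.

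Heavy-to-light ratio on the same dose:

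| b | Weights (kg) | X/Dose | As written | Dose per kg |
|---|---|---|---|---|
| 1 | 100 v 60 | 0.60 | 0.36 | 1.00 |
| 0.75 | 100 v 60 | 0.68 | 0.41 | 1.14 |
| 0.75 | 85 v 65 | 0.82 | 0.63 | 1.07 |
| 0.25 | 100 v 60 | 0.88 | 0.53 | 1.47 |
| 0 | 100 v 60 | 1.00 | 0.60 | 1.67 |

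**Between-subject CV.** By the usual log-normal formula, geometric CV = 100 × √(exp(0.25² + (e·s)²) − 1). Here e is the exponent, s is the SD of log weight, and 0.25 is an assumed residual log-SD. At b = 0.75, s = 0.13, as written: e·s = 1.75 × 0.13 = 0.2275; 0.0625 + 0.0518 = 0.1143; CV = 34.8%.

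| s (b = 0.75) | X/Dose | As written | Dose per kg |
|---|---|---|---|
| 0.10 | 26.6% | 31.2% | 25.5% |
| 0.13 | 27.3% | 34.8% | 25.6% |

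**Group comparisons.** Active groups have six subjects. A one-standard-error difference in mean log weight between two such groups is 0.13 × √(2/6) = 0.075. At b = 0.75 it shifts the ratio of geometric means by about 14% as written (exp(1.75 × 0.075) = 1.14), about 6% for X/Dose and about 2% for dose per kg.

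**The case against.** Five points can be made for leaving this alone.

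- **No decision depends on it.** The main parameters, the dose-normalised forms, CL/F, Vz/F, the food-effect ANOVA, Frel and the PK stopping criteria do not use these four quantities. The values can be recomputed from listed weights. This stands, and it caps the importance.
- **The intended formula is inferred.** No sentence says dose per kg for these parameters, and Table 2 is a dose table, not a normalisation rule. This is true, but the label, the mg/kg doses and the per-kg clearances all point the same way, and nothing supports a product.
- **Dose per kg is not always better than doing nothing.** It removes the weight effect fully only at b = 1. For b below 0.5 it leaves a larger effect than plain X/Dose, because 1 − b then exceeds b. At b = 0 the two forms introduce effects of equal size in opposite directions. This is correct, but for every b above zero the SAP form is still the worst of the three.
- **The sizes are illustrative.** Weights, spreads and b are assumed, and the 0.75 exponent concerns clearance, so it does not govern Cmax. A wider weight log-SD of 0.20 would give 45.1% as written. That is extreme here: BMI uniform over 18 to 30.1 gives about 0.15, or about 0.17 with an assumed height log-SD of 0.04. I do not rely on it.
- **The units disclose the product form.** A careful reader could notice it. That helps with detection but does not make the label true.

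**Conclusion.** The definition is wrong as written. The direction is algebra and needs no data: the formula multiplies a flat-dose exposure by a further 1/weight, so it enlarges any inverse weight effect and creates one where none exists. The size depends on assumptions. At b = 0.75, a 100 kg v 60 kg ratio of 0.68 becomes 0.41, and a geometric CV of 27.3% becomes 34.8% (residual log-SD 0.25, weight log-SD 0.13). That the intended form is dose per kg is a strong inference from the documents' own conventions, not a stated fact. The consequences are confined to exploratory listings and summaries. It should be corrected before the outputs are produced, but it does not threaten the trial's main conclusions.

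**What to change.** In SAP Appendix B, section 3.1.1, define all four parameters as X/(Dose/body weight) = X × body weight/Dose. Change the units to (ng/mL)/(mg/kg) for Cmax,norm and (h*ng/mL)/(mg/kg) for the three AUCs. Make the same edit in the repeated copy of the text and in the derivation program, using the Day -1 weight collected for this purpose. Before comparing norm values across parts, check which formula the Part 1 outputs used; the Part 1 SAP is not among the documents. The cost is four formula lines, their units and the matching code, with no new data.
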